5.4.2. QTc Stopping Criteria

If a subject that meets the corrected QT (QTc)¹ interval duration criteria below, study treatment(s) will be withheld.

- QT interval corrected for heart rate by Fridericia's formula ($QTcF = QT / \text{CubeRootRR}$) >500 msec
- Increase of QTcF by ≥ 60 msec from baseline
- For patients with underlying **bundle branch block**, follow the discontinuation criteria listed below:

| Baseline QTc with Bundle Branch Block | Discontinuation QTc with Bundle Branch Block |
|---------------------------------------|--|
| < 450 msec | > 500 msec |
| 450 – 480 msec | ≥ 530 msec |

¹Based on average QTc value of triplicate electrocardiograms (ECGs) to include manual over-read. For example, if an ECG demonstrates a prolonged QT interval, obtain 2 additional ECGs over a brief period (e.g., within approximately 10 minutes of the abnormal ECG, if possible, and approximately 10 minutes apart from each other), and then use the averaged QTc values of the 3 ECGs to determine whether the subjects should have study treatment(s) withheld.

If the QTc prolongation resolves to Grade 1 or baseline, the subject may be re-started on the study treatment(s) if the investigator and GSK Medical Monitor agree that the subject will benefit from further treatment.

The QTc should be based on single or averaged QTc values of triplicate electrocardiograms obtained over a brief (e.g., 5-10 minute) recording period.

5.4.3. Mental Status Stopping Criteria

Enrollment will be stopped upon the occurrence of any encephalopathy, unless clearly attributable to central nervous system disease involvement or intercurrent illness.

Study treatment will be held and neurology consult obtained if any of the 3 criteria below are met:

- A decrease of 3 points or more from baseline (pre-dose Day 1) Montreal Cognitive Assessment (MOCA) score (Section [7.3.7](#))

- Any MOCA score of <22
- Any other indication of early encephalopathy as determined by patient history or physical exam

The treatment may resume if one of the following criteria is met:

- A reversible cause other than study treatment is identified and both MOCA score and symptoms return to baseline (pre-dose Day 1).
- Evaluated by a neurologist and found to have no clear signs/symptoms of encephalopathy or other cognitive dysfunction. This is applicable only in the absence of decrease in MOCA score.

All treatment restarts must be approved by GSK medical monitor. The treatment should be permanently discontinued for subjects with documented symptoms with no other cause, even if they return to baseline (pre-dose Day 1).

5.5. Safety Management

5.5.1. Events of Special Interest

5.5.1.1. Hematologic Events

Any signs of bleeding, bruising and infection will be monitored closely throughout the study. Platelet transfusion will be administered following institutional guidelines and practices. Neutropenia and anemia management and fungal or bacterial prophylaxis will also follow institutional guidelines.

Transfusions are allowed throughout the study as clinically indicated.

Erythropoietin is not allowed on study.

The use of granulocyte stimulating growth factors is only allowed for treatment of febrile neutropenia and other life threatening infections.

5.5.1.2. Mental Status Change

When a subject presents with a possible indication of early encephalopathy, the subject should be admitted and study treatment held immediately. Below procedures should take place following the admission to support the diagnosis and/or exclude carcinomatous meningitis, unless contraindicated:

- Brain MRI scan with contrast
- Lumbar puncture with cytology analysis
- Electroencephalogram (EEG)
- Metabolic panel

5.5.2. Dose Adjustment for Non-Hematologic Toxicity

See [Table 3](#) below. Dose Adjustment Guideline for drug related non-hematologic toxicities based on worst grade.

Table 3 Dose Adjustment Guideline for Drug Related Non-Hematologic Toxicity

| Worst Grade | Dose Adjustment |
|-------------|--|
| G1 | No change in dose |
| G2 | Continue dosing with no change OR Consider holding GSK2879552 and/or azacitidine for up to 2 weeks for toxicity to resolve to baseline or \leq Grade 1, then continue at the same dose OR dose reduce GSK2879552 and/or azacitidine by 25-50%. |
| G3 and 4 | Hold GSK2879552 and/or azacitidine for up to 2 weeks for toxicity to resolve to baseline or \leq Grade 1, then dose reduce GSK2879552 and/or azacitidine by 25-50%. If no recovery to \leq Grade 1* or baseline after 14 days, patient should be withdrawn. |

*Note: Some AEs, such as rash and alopecia, may not be required to recover to Grade 1 or baseline. Additional AEs may be considered non-clinically significant and qualify for this exception if agreed upon by the GSK medical monitor.

If unexplained reductions in serum bicarbonate levels to <20 mEq/L occur, azacitidine dose should be reduced by 50% on the next course. Similarly, if unexplained elevations of BUN or serum creatinine occur, the next cycle should be delayed until values return to normal or baseline and the dose should be reduced by 50% on the next treatment course. A full dose of azacitidine will be administered in the subsequent treatment courses, once serum bicarbonate level returns to ≥ 20 mEq/L, and BUN and serum creatinine level returns to normal or baseline, and no other toxicities are apparent.

If the non-hematologic toxicity or event resolves to baseline or \leq Grade 1 within 14 days of stopping therapy, treatment with GSK2879552 and/or azacitidine may be restarted with at least **25%** dose reduction. For a non-DLT, the treatment with GSK2879552 and/or azacitidine could restart at a full dose, if deemed appropriate.

If the non-hematologic toxicity does not resolve to \leq Grade 1 or baseline within 14 days, the subject should be withdrawn from the treatment permanently. However, if the investigator and GSK Medical Monitor agree that further treatment will benefit the subject, treatment can restart with at least **25%** dose reduction of both drugs once the toxicity resolves to \leq Grade 1 or baseline.

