12.2. Appendix 2: Liver Safety Required Actions and Follow up Assessments

Phase I/II liver chemistry stopping and increased monitoring criteria have been designed to assure subject safety and evaluate liver event etiology (in alignment with the FDA premarketing clinical liver safety guidance).

<http://www.fda.gov/downloads/Drugs/GuidanceComplianceRegulatoryInformation/Guidances/UCM174090.pdf>.

Phase I/II liver chemistry stopping criteria and required follow up assessments

| Liver Chemistry Stopping Criteria – Liver Stopping Event | |
|---|--|
| ALT-absolute | ALT ≥ 5xULN |
| ALT Increase | ALT ≥ 3xULN persists for ≥4 weeks |
| Bilirubin^{1,2} | ALT ≥ 3xULN and bilirubin ≥ 2xULN (>35% direct bilirubin) |
| INR² | ALT ≥ 3xULN and INR>1.5, if INR measured |
| Cannot Monitor | ALT ≥ 3xULN and cannot be monitored weekly for 4 weeks |
| Symptomatic³ | ALT ≥ 3xULN associated with symptoms (new or worsening) believed to be related to liver injury or hypersensitivity |
| Required Actions and Follow up Assessments following Liver Stopping Event | |
| Actions | Follow Up Assessments |
| 
 • Immediately discontinue study treatment • Report the event to GSK within 24 hours • Complete the liver event CRF and complete an SAE data collection tool if the event also meets the criteria for an SAE² • Perform liver event follow up assessments • Monitor the subject until liver chemistries resolve, stabilize, or return to within baseline (see MONITORING below) • Do not restart/rechallenge subject with study treatment unless allowed per protocol and GSK Medical Governance approval is granted (refer to Appendix | 
 • Viral hepatitis serology⁴ • Blood sample for pharmacokinetic (PK) analysis, obtained approximately 48h after last dose⁵ • Serum creatine phosphokinase (CPK) and lactate dehydrogenase (LDH). • Fractionate bilirubin, if total bilirubin≥2xULN • Obtain complete blood count with differential to assess eosinophilia • Record the appearance or worsening of clinical symptoms of liver injury, or hypersensitivity, on the AE report form • Record use of concomitant medications on the concomitant medications report form including acetaminophen, herbal remedies, other over the counter medications |

| | |
|---|---|

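### Section 5.5.2 and Table 3 allow continuation or restart where the mental-status and liver stopping rules forbid or restrict it, and nothing says which governs

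*Protocol*

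**What the plan says.** Section 5.5.2 introduces Table 3 as a "Dose Adjustment Guideline for drug related non-hematologic toxicities based on worst grade". Grade 1 calls for no change. For Grade 2 the options begin with "Continue dosing with no change OR Consider holding GSK2879552 and/or azacitidine for up to 2 weeks" and end with a dose reduction. For Grade 3 and 4 the row reads "Hold GSK2879552 and/or azacitidine for up to 2 weeks for toxicity to resolve to baseline" or Grade 1, followed by a 25-50% reduction, with withdrawal if there is no recovery after 14 days.

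The text under the table is not tied to a grade. An event that resolves within 14 days of stopping may be followed by restart with a reduction of at least 25%, and then: "For a non-DLT, the treatment with GSK2879552 and/or azacitidine could restart at a full dose, if deemed appropriate". An event that does not resolve in that time can still be followed by a reduced restart once it does, if the investigator and the Medical Monitor agree.

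Section 5.5.2 has exceptions of its own. A note says that "Some AEs, such as rash and alopecia, may not be required to recover to Grade 1 or baseline", other events may be added with the Medical Monitor's agreement, and there are separate rules for low bicarbonate and for raised BUN or creatinine. None covers liver, QTc or mental-status events.

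The dedicated stopping rules sit elsewhere:

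- **Mental status (Section 5.4.3).** Treatment is held, with a neurology consult, on a MOCA or clinical trigger. Every restart needs Medical Monitor approval. The section closes: "The treatment should be permanently discontinued for subjects with documented symptoms with no other cause, even if they return to baseline (pre-dose Day 1".
- **Liver (Section 5.4.1.1, Appendices 2 and 3).** A stopping event means immediate discontinuation. Appendix 2 adds: "Do not restart/rechallenge subject with study treatment unless allowed per protocol and GSK Medical Governance approval is granted". Section 5.4.1.1 and Appendix 3 add separate consent and, where required, ethics approval.
- **QTc (Section 5.4.2).** Treatment is withheld. The section then opens a way back: "the subject may be re-started on the study treatment(s) if the investigator and GSK Medical Monitor agree". The conditions are recovery (baseline or Grade 1) and an expected benefit.

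**The concern.** Drug-related encephalopathy and drug-related liver injury are both non-haematologic toxicities, so Section 5.5.2 covers them as written. A site that works from the dose-adjustment table reaches an action that another section forbids or makes conditional on further approvals. This goes beyond missing detail, because Section 5.5.2 states a restart rule of its own.

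The stakes are highest for mental status. Section 2.2.5 reports encephalopathy in 3 of 18 subjects of the first-in-human study, one case fatal. The amendment log attributes the update of Section 5.4.3 to language mandated by the FDA. Section 5.5.2 carries no reference to that section.

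**Working it through.** No arithmetic is involved. The check takes one event at a time and reads off the action that each passage gives.

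| Event | Section 5.5.2 / Table 3 | Dedicated rule |
|---|---|---|
| Drug-related mental-status symptoms, no other cause, Grade 1 | No dose change | 5.4.3: hold and neurology consult; permanent discontinuation |
| Same, Grade 2 | May continue unchanged | As above |
| Same, dosing stopped, resolved within 14 days | Restart permitted, reduced or (non-DLT) at full dose | 5.4.3: permanent discontinuation despite recovery |
| Drug-related liver stopping event, resolved within 14 days | Restart permitted; no approval named | Governance approval, separate consent and, if required, ethics approval first |
| Same, not resolved within 14 days | Withdraw, or restart after resolution if investigator and Medical Monitor agree | As above |
| Drug-related QTc event, Grade 3 or 4 | Hold until Grade 1 or baseline, then restart: reduced per the table, or full dose if a non-DLT | 5.4.2: withhold until Grade 1 or baseline, then possible restart; no dose stated |

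**Mental status.** The third row needs no grading table. Section 5.4.3 offers two ways to resume. One requires a reversible cause other than study treatment. The other requires a neurologist to find no clear signs, and applies only if the MOCA score has not fallen. A subject with documented symptoms and no other cause is then covered by the permanent stop. Section 5.5.2 permits restart for that same subject. The full-dose option is wide, because Section 4.3.3 limits DLTs to the first 28 days: any event after Day 28 is a non-DLT.

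**Liver.** Which Table 3 row applies depends on CTCAE cut-offs that the protocol does not print. The conflict over restart does not, because the restart text under the table is not tied to grade. Even its most restrictive case asks only for agreement between investigator and Medical Monitor, which is not the set of approvals in Section 5.4.1.1 and Appendix 3.

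**QTc.** For a Grade 3 or 4 event both passages withhold, wait for the same recovery and then allow restart. Section 5.4.2 is silent on dose, and silence is not a contradiction. A clash between continuing and withholding would need a CTCAE grade for the QTc triggers, which the protocol does not give.

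**Precedence.** Section 5.5.2 does not mention Sections 5.4.1 to 5.4.3, and they do not mention it. Section 5.4 refers to Section 4.7 for permanent discontinuation. Section 4.7 names the liver criteria but not the mental-status rule.

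**The case against.** The strongest reply is that a competent reader applies the specific rule before the general one. Table 3 is labelled a guideline, while Sections 5.4.1 to 5.4.3 are headed as stopping criteria and worded as directives. Section 5.5.1.2, shortly before Table 3, requires admission and an immediate hold on possible early encephalopathy, and the risk table in Section 4.11.1 repeats the hold for MOCA triggers. Section 4.7 already lists the liver criteria as ending treatment. A MOCA fall is also a score trigger independent of causality, so Table 3 reaches it only if it is recorded as drug-related toxicity.

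Most of this stands, and it makes wrongful continued dosing less likely in practice. It does not remove the conflict: Section 5.5.1.2 is silent on restart, Section 4.7 omits the mental-status stop, and no sentence states precedence.

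Four stronger readings are tempting and are not supported:

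- **That all three stopping rules conflict with Table 3.** The QTc passages do not clearly do so, as shown above.
- **That Section 5.5.2 has no exceptions at all.** It has several; they do not cover these events.
- **That the words about what the protocol allows, in Appendix 2, turn Table 3 into permission to restart after a liver event.** The condition is joint: governance approval is needed as well, and the sentence sends the reader to Appendix 3.
- **That the recommended phase 2 dose is compromised.** Decisions in Part 1 count DLTs, which Section 4.3.3 defines separately. There is one narrow route: drug-related toxicity that prevents at least 75% of intended doses is a DLT, which for daily GSK2879552 is 0.75 × 28 = 21 doses. A lower-grade mental-status event could then count or not, depending on which section the site followed. That is a possibility, not a demonstrated effect.

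**Conclusion.** The conflict is real for two of the three dedicated stopping rules. For drug-related mental-status symptoms with no other cause, the protocol gives instructions that run from no dose change to permanent discontinuation, and it permits restart after recovery in one section while ruling it out in another. For liver stopping events, the conflict is over the approvals and consent required before restart. For QTc, only the restart dose is unclear.

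The mental-status conclusion rests on the text alone, given that the investigator judges the event drug-related. For liver, the Table 3 row depends on grade cut-offs not printed in the protocol, but the restart conflict does not. The documents do not show how often a site would follow the wrong passage, and the specific-rule reading is likely in practice. The point should be corrected because it concerns a key safety risk of the compound and the correction is small.

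**What to change.** State in Section 5.5.2 and in the Table 3 heading how events meeting Section 5.4.1 (with Appendices 2 and 3), 5.4.2 or 5.4.3 are handled relative to Table 3. Add cross-references in both directions, and have Section 4.7 refer to Section 5.4.3 as it already refers to the liver criteria. The same statement can settle what restart dose, if any, Section 5.5.2 implies for QTc events. The sponsor decides the clinical rule; the need here is that the passages agree.

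The cost is one sentence and a few cross-references at the next amendment. No sample size, endpoint or analysis changes.

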4.3.3. Dose Limiting Toxicities

An event will be considered a DLT if it occurs within the first 28 days of treatment, and meets one of the following criteria unless it can be clearly established that the event is unrelated to treatment. Subjects unable to receive at least 75% of scheduled doses (of both agents, at the intended strength) for reasons other than toxicity (e.g., acute illness, disease progression) will not be evaluable for DLT purposes:

- Grade 4 thrombocytopenia associated with clinically significant bleeding
- Any Grade 3 or greater non-hematologic toxicity
- Fatigue, asthenia, nausea, vomiting or new electrolyte disturbance that respond to standard medical care within 72 hours are exceptions
- Any toxicity considered drug related that in the judgment of the investigator and GSK Medical Monitor is dose-limiting
- Drug related toxicities that prevent subjects from taking $\geq 75\%$ of the intended doses during the first 28 days of treatment
- Treatment delay of 14 days or greater due to unresolved drug-related toxicity

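### Section 5.5.2 gives two answers on restarting after a resolved drug-related Grade 3-4 non-haematologic toxicity: Table 3 requires a reduction, while the text below it allows full dose for any non-DLT, whatever the grade

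*Protocol*

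**What the plan says.** Section 5.5.2 introduces Table 3 as a "Dose Adjustment Guideline for drug related non-hematologic toxicities based on worst grade". In the Grade 2 row, a subject who has been held may "then continue at the same dose OR dose reduce GSK2879552 and/or azacitidine by 25-50" percent. The Grade 3 and 4 row has no same-dose option: the drug is held for up to two weeks until recovery, "then dose reduce GSK2879552 and/or azacitidine by 25-50%. If no recovery to" Grade 1 or baseline after 14 days, the subject should be withdrawn.

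The text below the table restates the default for events that recover within 14 days, namely restart with a reduction of at least 25%, without naming a grade. It then adds the exception: "For a non-DLT, the treatment with GSK2879552 and/or azacitidine could restart at a full dose, if deemed appropriate".

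Section 4.3.3 defines the label on which that exception turns: "An event will be considered a DLT if it occurs within the first 28 days of treatment" and meets a listed criterion. The criteria include "Any Grade 3 or greater non-hematologic toxicity", with this carve-out: "Fatigue, asthenia, nausea, vomiting or new electrolyte disturbance that respond to standard medical care within 72 hours are exceptions". They also include a judgement clause, "Any toxicity considered drug related that in the judgment of the investigator and GSK Medical Monitor is dose-limiting", which sits under the same 28-day limit.

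**The concern.** The table sorts events by severity. The sentence below it sorts them by DLT status, a label built for Cycle 1 dose-escalation decisions that says nothing about how severe a later event is. Where the two sortings disagree, a site has two instructions for the same subject: reduce, or resume at full dose if that seems appropriate. What is at stake is re-exposure at an unreduced dose after a Grade 3 or 4 toxicity, and different handling of like cases across sites. This is a matter of subject safety and of consistency within the protocol, not of inference.

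**Working it through.** No sample-size, power or error-rate figure is involved. The check sets Section 5.5.2 beside Section 4.3.3 and follows one kind of event through both: a drug-related non-haematologic toxicity that has recovered to Grade 1 or lower, or to baseline, within 14 days.

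| Event | DLT under 4.3.3? | Table 3 | Text below Table 3 | Agree? |
|---|---|---|---|---|
| Grade 2, not otherwise dose-limiting | No | Same dose or reduce | Full dose allowed | Yes |
| Grade 3-4, Days 1-28, not a 72-hour exception | Yes | Reduce 25-50% | Reduce at least 25% | Yes, both reduce |
| Grade 3-4, Days 1-28, 72-hour exception and no other DLT criterion met | No | Reduce 25-50% | Full dose allowed | No |
| Grade 3-4, onset Day 29 or later | No | Reduce 25-50% | Full dose allowed | No |

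The last row follows because the 28-day limit governs every criterion in Section 4.3.3, including the judgement clause. An investigator and Medical Monitor who regard a Day 29 event as dose-limiting still cannot make it a DLT under that definition. A Grade 4 event outside the exceptions must be followed by a reduction if it starts on Day 28, but may be followed by full dose, on the text, if it starts on Day 29.

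**Dose contrast, Arm A.** Inputs: the planned 2 mg once daily (Section 4.3.1) and the 25-50% reduction (Table 3).
- Smallest reduction: 2 mg × (1 − 0.25) = 1.5 mg.
- Largest reduction: 2 mg × (1 − 0.50) = 1 mg.
- Text: 2 mg.

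The two instructions therefore give 1-1.5 mg and 2 mg.

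**Options in Arm B.** The Grade 3 and 4 row says GSK2879552 and/or azacitidine. Read as written, it permits three restarts: both drugs reduced, only GSK2879552 reduced, or only azacitidine reduced. The sentence below adds one more, both unreduced. No single-drug dose contrast can be drawn, because Table 3 already allows either drug to resume at full dose if the other is reduced.

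**What lies outside.** Liver, QTc and mental-status events, unexplained changes in bicarbonate, BUN or creatinine, haematologic toxicity, and events not recovered within 14 days all have their own rules.

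**The case against.** The best defence is that this is a rule followed by a permissive exception. Table 3 is titled a guideline, the sentence says only that treatment could restart at full dose, and it applies only after a hold and recovery. Nobody is obliged to resume at full dose, and an investigator who always reduces after Grade 3-4 satisfies both texts. All of that stands, and it limits the finding: the reduction becomes optional; it is not forbidden.

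A second defence is that the sentence was meant for Grade 2. That is plausible. The default just before it names no grade, so without the exception it would take away the same-dose option that Table 3 gives Grade 2. But the sentence does not say so. Reading non-DLT as an event below the DLT grade criteria on any day would also remove the jump at Day 29, but Section 4.3.3 does not define the term that way.

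Four stronger readings are tempting and should not be drawn:
- **That calendar day alone decides.** Within Days 1-28 the DLT label does track grade and type of event, and the 72-hour exceptions show that the conflict does not begin only at Day 29.
- **That most of treatment is affected.** Dosing can run well past Day 28, but a share of time is not a share of events. The protocol gives neither an expected treatment duration nor a late-event rate from which to estimate affected subjects.
- **That Section 4.7 already settles the standard.** Its condition about recent Grade 3/4 events concerns treatment beyond progression, which is a different benefit-risk decision.
- **That all combination exposure after crossover is outside the DLT window.** The protocol does not say whether that window restarts at crossover, so the point cannot rest on it.

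**Conclusion.** The conflict is real, and nothing elsewhere in the protocol resolves it. It covers drug-related Grade 3-4 non-haematologic events that recover within 14 days and have no rule of their own, when onset is on Day 29 or later or when the event falls under the 72-hour exceptions within Days 1-28. Its size per event in Arm A is 1-1.5 mg against 2 mg, assuming that the planned 2 mg is the dose in use. In Arm B it is one additional option, both drugs unreduced. The conclusion rests on the literal 28-day limit in Section 4.3.3 and on the absence of any grade limit in the full-dose sentence. How many subjects would be affected cannot be estimated from the document. Part 1 DLT counts and the Part 2 test of clinical benefit rate do not depend on it. It should be corrected because the instruction governs re-dosing after severe toxicity and the correction is small.

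**What to change.** In the text of Section 5.5.2, replace the opening words of the full-dose sentence (*For a non-DLT*) with: *For a Grade 2 event, or an event covered by the 72-hour exceptions in Section 4.3.3, regardless of day of onset*. Add the same exception to the Grade 3 and 4 row of Table 3, so that table and text agree. All other Grade 3-4 events then restart with at least a 25% reduction at any time on treatment.

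Keep the exception as Section 4.3.3 has it, attached to Grade 3 or greater; nothing here calls for narrowing it to Grade 3. The and/or for Arm B can stay as it is: the change removes only the option of resuming both drugs unreduced after a Grade 3-4 event outside the exceptions.

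The cost is a wording change in one section, with no added subjects, visits or procedures. The downside is slightly less investigator discretion over late Grade 3-4 events.
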